10.7. Other Assessments

10.7.1. Quality of Life and Health-Related Outcomes

QoL questionnaires should be completed prior to study treatment administration on the days when QoL questionnaire is completed.

EORTC QLQ-C30: The QLQ-C30 is a validated, patient self-administered instrument for assessing the health-related QoL of cancer patients participating in international clinical studies. It is a questionnaire containing both multi-item and single scales, including five functional scales (physical, role, emotional, social and cognitive), three symptom scales (fatigue, nausea & vomiting and pain) and a global health status/QoL scale and six single items (dyspnea, insomnia, appetite loss, constipation, diarrhea and financial difficulties).

EuroQoL EQ-5D-5L: The EQ-5D-5L is a validated, patient self-administered instrument used for multiple health conditions and treatments, to provide a simple descriptive profile and a single index value of health status.

10.7.2. Treatment Assignment Query

Prior to unblinding, the patient and the Investigator will be asked which study treatment (active [selinexor] or placebo) they believe the patient received during blinded study treatment.

Specifically:

- After PD but prior to unblinding, the patient and the Investigator will be asked which study treatment (active [selinexor] or placebo) they believe the patient received during blinded study treatment and their responses will be recorded.
- If blinded study treatment is discontinued without PD, query should be performed at the time that blinded study treatment is discontinued and prior to unblinding. See Section 11.3.
- If unblinding is required for clinical management of a clinically important SAE leading to discontinuation of study treatment and knowledge of the received study treatment is required for clinical management and treatment of the SAE, query should be performed prior to unblinding.

10.7.3. Nutritional Consultation

It is strongly recommended that the Investigator, or his/her designee, provide patients with a nutritional consultation to discuss any food recommendations and strategies for managing potential nausea and appetite changes experienced with selinexor. This consultation does not need to be performed by a nutritionist.

During blinded study treatment, the nutritional consultation should occur on C1 D1 before the first dose of blinded study treatment (or within the Screening Period).

During treatment with open-label selinexor, the nutritional consultation should occur on C1 D1 before the first dose of open-label selinexor for patients in the placebo arm who cross over to open-label selinexor. The nutritional consultation is not required at C1 D1 of open-label selinexor treatment for patients in the selinexor arm who continue on selinexor but as open-label treatment.

[figure not shown]
The nutritional consultation may be also performed at any time during the study, as necessary.

10.7.4. Collection of Information on Antineoplastic Therapy

[figure not shown]
Information on any antineoplastic therapies used after discontinuation of study treatment will be collected at the EoBT Visit (Section 9.1.6), the EoT Visit (Section 9.2.4), Safety Follow-up Calls (Section 9.1.7 and Section 9.2.5), and during Survival Follow-up (Section 9.1.8 and Section 9.2.6).

For patients who progress on post-study treatment antineoplastic therapy, the Investigator should enter the date of progression from the medical record in the eCRF if that information is available to the Investigator.

CCI

CCI

CCI

[figure not shown]
CCI

[figure not shown]
CCI

CCI

CCI

11. DISCONTINUATION AND UNBLINDING CRITERIA

11.1. Early Termination of the Study

The study may be terminated at the sole discretion of the Sponsor for any reason, including medical or ethical reasons affecting the continued performance of the study, or difficulties in the recruitment of patients. If this occurs, the Sponsor will notify IECs, IRBs, Investigators, and regulatory authorities.

11.2. Discontinuation of Study Treatment and/or Withdrawal of Patients from the Study

The Investigator may remove a patient from study treatment for any of the following reasons:

- PD as defined by the central reader by RECIST v. 1.1 (see exception for patients who may derive benefit from continued treatment with selinexor in Section 7.2.4)
- Clinical progression as determined by the Investigator in consultation with the Sponsor (must be documented by radiographic imaging and assessed by the central reader)
- Unacceptable AEs or toxicity that cannot be managed by supportive care
- Significant deviations from inclusion/exclusion criteria
- Misuse of study treatment (eg, deliberate overdosing by patient)
- Missed / unscheduled / off-schedule / incomplete / incorrect assessments that result in patients being put at risk
- Any other medically appropriate reason or significant protocol violation, in the opinion of the Investigator.

The Investigator must remove a patient from study treatment for any of the following reasons:

- Patient withdraws consent to continue study treatment
- Pregnancy
- Use of radiation to treat the patient's liposarcoma (see Section 12.2.5.3)

Patients may discontinue study treatment for any reason. Patients who decide to discontinue study treatment should be encouraged to continue in the study so that follow-up information on PD and survival status may be obtained. Patients who discontinue study treatment but continue follow-up will be followed for anti-neoplastic therapy initiation and **CCI** every 3 months. These patients will be included in the ITT analysis if they are in Phase 3.

Patients may withdraw consent and decline further participation in the study at any time. Patients who withdraw consent must be withdrawn from the study.

Any patient who does not withdraw from the study but who stops attending study visits and does not respond to three documented contact attempts will be considered lost to follow-up.

The Investigator must determine the primary reason for a patient's discontinuation of study treatment/withdrawal from the study and record this information on the eCRF.

11.3. Unblinding

11.3.1. Unblinding of Treatment Assignment During Blinded Study Treatment

Patients who have PD per RECIST v. 1.1 will discontinue blinded study treatment and their treatment assignment will be unblinded. Unblinding will take place within 14 days of the last blinded dose and may occur on or before the patient's EoBT Visit (Section 9.1.6). Only the patient, the Investigator at the study site, and key Sponsor team members as specified to monitor the conduct of the study will be unblinded to the treatment assignment.

Treatment assignments for patients who discontinue blinded study treatment without determination of PD by the central reader (including patients who discontinue blinded study treatment for reasons other than PD) will not be unblinded until the primary PFS analysis at the end of Phase 3 and these patients are not allowed to receive open-label selinexor.

- **Exception:** Treatment assignment may be unblinded in the event of a clinically important SAE *only* if unblinding is required for clinical management of a clinically important SAE leading to discontinuation of study treatment and knowledge of the received study treatment is required for clinical management and treatment of the SAE. If the patient is on the placebo arm and PD has not been documented, the patient will not be eligible to receive open-label selinexor.

11.3.2. Unblinding of Treatment Assignment for All Patients at the Primary PFS Analysis at the End of Phase 3

Once the required number of PFS events for the primary PFS analysis at the end of Phase 3 are observed, unblinding of treatment assignment for all patients will take place and the primary PFS analysis will be conducted. Patients who did not have PD at the time of unblinding will 1) continue selinexor but as open-label treatment if they were in the selinexor arm, or 2) have the option to cross over to open-label selinexor if they were in the placebo arm.

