9.1.6. End of Blinded Treatment Visit; Return to the Clinic

At the time a patient permanently discontinues blinded study treatment or has PD prior to unblinding of all patients at the end of Phase 3 (ie, when the required number of PFS events for the primary PFS analysis are observed), a visit should be scheduled as soon as possible (within 14 days), at which time all of the assessments listed for the End of Blinded Treatment (EoBT) Visit will be performed. Study procedures will be performed ≤ 14 days after the last dose of study treatment, as specified in Table 1. An EoBT CRF page will be completed, giving the date and reason for stopping the study treatment. Patients lost to follow-up should be recorded as such on the appropriate eCRF.

For patients proceeding to open-label selinexor, the EoBT Visit will serve as the baseline for the open-label treatment phase. After the unblinding following the PFS analyses, patients in the selinexor arm who are continuing on selinexor but as open-label treatment must complete their EoBT Visit before their next scheduled selinexor dose.

- Informed consent for open-label selinexor (only for patients proceeding to open-label selinexor) and Assent Form for adolescent patients (permitted only in countries in

which adolescents have been approved by the national/local regulatory/ethical authority)

- Physical examination and vital signs (blood pressure, pulse, and body temperature) (Section 10.6.1.1)
- Weight, height, and BSA (Section 10.6.1.2)
- ECOG performance status assessment (Section 10.6.1.3)
- 12-lead ECG (Section 10.6.1.4)
- Urinalysis (Section 10.6.2.1)
- Hematology (Section 10.6.2.1)
- Complete serum chemistry (Section 10.6.2.1)
- Coagulation tests (Section 10.6.2.1)
- Serum hCG pregnancy test (females of childbearing potential only). Females of childbearing potential who are proceeding to open-label selinexor must have a negative serum hCG pregnancy test at the EoBT Visit (or within 3 days before the first dose of open-label selinexor). (Section 10.6.2.2)

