- Tumor biopsy for patients who were in the placebo arm and are crossing over to open-label selinexor only. If the patient has archival material (ie, of DDLS tissue) collected at Screening, Cycle 1 Day 22, or Cycle 2 Day 1 within 12 months prior to the first dose of open-label selinexor, that sample may substitute for the biopsy. Patients in the selinexor arm who continue on selinexor but as open-label treatment are not required to have an additional tumor biopsy at the EoBT Visit. See Section 10.11.3.
- Imaging to evaluate site of disease and distant sites (abdomen, pelvis, chest)
 - Phases 2 and 3: CT (preferred) or MRI scan for tumor measurement (if \geq 4 weeks since last prior scan AND required to document disease or clinical progression) for assessment of liposarcoma. Patients in the placebo arm who have clinical progression must have subsequent radiographic progression determined by the central reader in order to receive open-label selinexor.
- Assessment of progression/extent of liposarcoma by RECIST v. 1.1 (2) if tumor (CT/MRI) scan is performed.
- Treatment assignment query of patients and Investigators (if not performed at a previous visit; query after PD but prior to unblinding) (Section 10.7.2).
- QoL questionnaires (EORTC QLQ-C30 and EuroQoL EQ-5D-5L) (Section 10.7.1)
- AEs/SAEs
- Concomitant medications
- Information on any antineoplastic therapies used since discontinuation of blinded study treatment

9.1.7. Safety Follow-up Phone Call (30 Days [+7 days] after last dose of study treatment)

Only for patients NOT proceeding to open-label selinexor.

At a minimum, all patients who discontinue study treatment, including those who refuse to return for an EoBT Visit, will be contacted for safety evaluations during the 30 days (+7 days) following the last dose of study treatment. Every effort should be made to contact the patient (or the patient's family) by telephone or by sending appropriate correspondence (eg, certified letter or email).

During this patient contact the most important information to be obtained includes the following:

- Overall medical condition of the patient and status of their liposarcoma
- AEs, including follow-up on any AEs that were not resolved at the EoBT Visit

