4.2.2.2. QLQ-C30

QLQ-C30 contains 30 questions and includes five functional scales (Physical, Role, Emotional, Social, and Cognitive Functioning), three symptom scales (Fatigue, Nausea/Vomiting and Pain) and a Global Health Status/QoL scale, and six single-item symptom items (dyspnoea, insomnia, appetite loss, constipation, diarrhoea and financial difficulties). The principle for scoring these scales is the same: 1. Calculate the mean of the items that contribute to the scale; this is the raw score. 2. Use a linear transformation to standardise the raw score, so that scores range from 0 to 100.

For functional scales and the global health status/QoL, a higher score represents a better level of functioning (better health status); for symptom scales/items, a higher score represents a higher level of symptomatology/problems (worse health status).

The missing data will be handled based on EORTC QLQ-C30 scoring manual (Fayers et al., 2001). The raw score (mean of the items that contribute to the scale) will only be calculated if at least half of the items (i.e., 3 of 6 items, or 3 of 5 items) from the domain have been answered. As a result, none of the single-item measures will be imputed.

The actual value and change from baseline before initiating a new antineoplastic treatment will be summarized using descriptive statistics over time for each of the five functional scales, three symptom scales and six items, and the global health status/QoL scale.

QLQ-C30 analyses will be summarized by treatment arm among Ph3-ITT, Ph3-PP, and Ph2-ITT populations. For exploratory purpose, QLQ-C30 will also be summarized in Ph3-OL and Ph2-OL populations, in which changes from baseline will be calculated using baseline values for the open-label period, i.e., last assessment on or before the start of open-label treatment.

Table 4-2 Scoring the QLQ-C30 version 3.0

	Scale	Number of items	Item range*	Version 3.0 Item numbers	Function scales
Global health status / QoL					
Global health status/QoL (revised) [†]	QL2	2	6	29, 30	
Functional scales					
Physical functioning (revised) [†]	PF2	5	3	1 to 5	F
Role functioning (revised) [†]	RF2	2	3	6, 7	F
Emotional functioning	EF	4	3	21 to 24	F
Cognitive functioning	CF	2	3	20, 25	F
Social functioning	SF	2	3	26, 27	F
Symptom scales / items					
Fatigue	FA	3	3	10, 12, 18	
Nausea and vomiting	NV	2	3	14, 15	
Pain	PA	2	3	9, 19	
Dyspnoea	DY	1	3	8	
Insomnia	SL	1	3	11	
Appetite loss	AP	1	3	13	
Constipation	CO	1	3	16	
Diarrhoea	DI	1	3	17	

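### The end-of-blinded-treatment QoL forms may be completed after the patient learns the treatment arm, and the SAP neither excludes nor flags those records

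*Protocol*

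**What the plan says.** **Disclosure.** For a patient with PD by central reading, Protocol 11.3.1 states: "Unblinding will take place within 14 days of the last blinded dose and may occur on or before the" patient's EoBT Visit. The respondent is one of those informed: "Only the patient, the Investigator at the study site, and key Sponsor team members" are named. Figure 2, footnote 2, repeats the timing. At the primary PFS analysis, Figure 3, footnote 1, lets disclosure fall before the EoBT Visit or during it.

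**Questionnaires.** Protocol 9.1.6 lists among the EoBT procedures "QoL questionnaires (EORTC QLQ-C30 and EuroQoL EQ-5D-5L) (Section 10.7.1"). The visit has the same 14-day limit as unblinding: procedures are due no more than 14 "days after the last dose of study treatment, as specified in Table 1". The only ordering rule for QoL is in Protocol 10.7.1, repeated in the Table 1 QoL footnote: "QoL questionnaires should be completed prior to study treatment administration on the days when QoL questionnaire is completed".

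**The one item ordered against unblinding.** Protocol 10.7.2 says of the treatment-assignment query: "After PD but prior to unblinding, the patient and the Investigator will be asked which study treatment" they believe was given.

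**Analysis.** SAP 4.2.2.2 says of QLQ-C30: "The actual value and change from baseline before initiating a new antineoplastic treatment will be summarized using descriptive statistics over time". SAP 4.2.2.3 applies the same cut-off to EQ-5D-5L. Both are summarized by randomized arm in Ph3-ITT, Ph3-PP and Ph2-ITT.

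**The concern.** QoL is a stated Phase 3 secondary objective, and the two instruments are self-reported. The protection that blinding gives to a self-report ends when the patient learns the arm. News of progression reaches both arms, so by itself it need not separate them. Knowledge of the arm can: one patient hears that the treatment was placebo and that open-label selinexor is available, another that the disease progressed on selinexor.

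The protocol recognizes this problem for the treatment-assignment query and places it before unblinding. It does not do so for the two questionnaires completed around the same time. If the form follows disclosure, the last value counted as blinded is an unblinded one, and it enters the by-arm summary unmarked. What is at stake is how the QoL comparison around progression can be interpreted, not the primary conclusion of the trial.

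**Working it through.** The documents give no figure to reproduce here. The check traces the order of events and then counts forms from the schedule.

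**1. Is disclosure before the form permitted?** Yes. Unblinding and the EoBT Visit share a limit of 14 days after the last blinded dose (Protocol 11.3.1 and 9.1.6), and unblinding may come first. No QoL rule intervenes, since completing a form before dosing is compatible with disclosure an hour or a week earlier.

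**2. Is it a remote possibility?** Not obviously. Several EoBT procedures in Protocol 9.1.6 depend on the arm: the biopsy applies only to placebo patients crossing over, open-label consent is listed there, and selinexor-arm patients continuing after the general unblinding must complete the visit before their next dose. A site therefore has reason to know the assignment by or during the visit. The documents do not say how often the form comes second.

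**3. Does the analysis remove such records?** No. The cut-off in SAP 4.2.2.2 and 4.2.2.3 is new antineoplastic therapy. The EoBT Visit is the baseline for open-label treatment (Protocol 9.1.6), so its form normally precedes that cut-off and stays in. The repeated-measures model in Protocol 14.3.4.2.2 excludes no visit either. The same record can also serve as the open-label baseline, because Protocol 9.2.1 collects QoL at the first open-label visit only if it was not done at EoBT.

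**4. Who is exposed?** Patients with central PD, patients on blinded treatment at the primary PFS analysis, and patients unblinded under the SAE exception. Those who stop without central PD otherwise stay blinded until the primary analysis (Protocol 11.3.1). A rough upper bound on the first group at the primary analysis is 209 PFS events (SAP 1.1) over 285 Phase 3 patients randomized (SAP 1.1): 209/285 = 73.3%. The true share affected is lower to the extent that PFS events are deaths or that forms were completed before disclosure.

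**5. What share of a patient's forms is the EoBT form?** QoL is collected on Day 1 of Cycle 2 and of every later 6-week cycle, and at EoBT (Table 1). With *k* on-treatment Day 1 forms up to the PD scan, the share is 1/(*k* + 1).

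| PD found at | *k* | Post-baseline forms | EoBT share |
|---|---|---|---|
| Week 6 | 1 | 2 | 1/2 = 50% |
| Week 12 | 2 | 3 | 1/3 = 33% |
| Week 18 | 3 | 4 | 1/4 = 25% |
| Week 24 | 4 | 5 | 1/5 = 20% |

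This assumes that all forms are completed and that the EoBT Visit comes after the PD scan visit and before the next Day 1 form. It is a per-patient count of forms that could be affected, not of forms that are.

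**6. A related gap.** SAP 4.1.1 and 4.2.2.4 count open-label selinexor as new antineoplastic therapy for PFS and ORR. The QoL sections do not say whether it counts, and SAP 2.4 says it does not when defining periods for selinexor-arm patients who continue. Later open-label forms from those patients could therefore also enter the by-arm summary.

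**The case against.** The strongest reply is that the protocol permits disclosure before the form but does not require it. That stands. A reader might infer that the by-arm QoL comparison does contain unblinded self-reports. The documents show only that such records are not kept out.

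A reader might also multiply the shares above by an assumed effect of knowing the arm. A shift of 5 to 10 points on the 0 to 100 scale, for example, would give 0.20 × 5 = 1 point up to 0.50 × 10 = 5 points in an average over visits. This is not supported:

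- The shift is pure assumption, and nothing in the documents shows that the two arms would move in opposite directions.
- The upper figure needs every patient in both arms to progress at week 6 and to be told before the form.
- The SAP plans descriptive statistics over time, not an average over visits. If EoBT is shown as its own time point, the Day 1 summaries are untouched. The SAP does not say how EoBT is mapped for QoL, because the windows in SAP 2.7 are for safety data. Averaging could arise under the protocol's mixed model, which the SAP's QoL sections do not carry forward.

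Nor does every progressing patient have the visit: Protocol 9.1.7 provides for patients who decline it. For the general unblinding, SAP 1.6 ties the interim lock to the same 209 events, and the documents do not state whether those EoBT forms fall before the data cut.

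Finally, QoL is outside the testing hierarchy (SAP 4.2.1 and 4.4), and SAP 4.2 already advises caution with nominal secondary p-values. This limits the weight of the point. It does not close the gap in the sequence.

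**Conclusion.** The point holds as a defect of sequence and of data handling. The protocol allows the patient to learn the arm before completing the EoBT questionnaires, and the SAP has no rule to exclude or identify the records that result. For a patient whose PD is found between weeks 6 and 24, the form concerned is 1 of 2 to 1 of 5 post-baseline forms, under the completeness and timing assumptions stated above.

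The frequency of prior disclosure, and the size and direction of any bias, cannot be derived from the documents. PFS by central review and OS are not affected. The point is worth acting on because QoL is a stated secondary objective and the remedy is small. It does not show that the QoL results are biased.

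**What to change.** **Protocol 9.1.6, 10.7.1 and the Table 1 QoL footnote.** Require both questionnaires to be completed before the assignment is disclosed, together with the existing treatment-assignment query. No new visit or procedure is needed. All 285 Phase 3 patients had been randomized when the SAP was written (SAP 1.1), so this helps only those still on blinded treatment.

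**SAP 4.2.2.2 and 4.2.2.3.** Flag every QoL record dated on or after the patient's unblinding date, including same-day records whose order is unknown, since dates alone cannot order events within a day. Keep the planned summary of all records and add a sensitivity summary without the flagged ones. The flag also catches forms after unblinding under the SAE exception and later open-label forms from selinexor-arm patients. It assumes that the unblinding date is available for each patient.

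Dropping the flagged records from the main summary is not advised. It would remove QoL data selectively at progression, and unequally if progression rates differ by arm.

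**Cost.** A little more analysis work, and fewer records around progression in the sensitivity summary.
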